## 6. GENERAL STATISTICAL CONSIDERATIONS

### 6.1. General Principles

Continuous variables will be summarized using appropriate descriptive statistics such as n (non-missing sample size), mean/geometric mean, standard deviation, median, maximum, and minimum. The number (n) and percentages (%; based on the non-missing sample size) of observed levels will be reported for all categorical measures. In general, all data will be listed, sorted by treatment group and participant, and when appropriate by visit number within participant. All summary tables will be structured with a column for each treatment in the order (1 $\mu$ g CJC2, 1 $\mu$ g CJC2+ALFQ, 3 $\mu$ g CJC2, 3 $\mu$ g CJC2+ALFQ, 10 $\mu$ g CJC2, 10 $\mu$ g CJC2+ALFQ) and will be annotated with the total population size relevant to that table/treatment group, including any missing observations.

Confidence intervals for Geometric Mean Titer (GMT) and Geometric Mean Fold-Rise (GMFR) will be calculated using a student's t distribution. Confidence intervals for proportions of participants will be exact CIs using the Clopper-Pearson method.

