## 6.5. Missing Data

All attempts will be made to collect all data per protocol. As missing data are expected to be minimal, no imputation will be performed for missing values. Any data point that appears to be erroneous or inexplicable based on clinical judgment will be investigated as a possible outlier. If data points are identified as outliers, sensitivity analyses will be performed to examine the impact of including or excluding the outliers. Any substantive differences in these analyses will be reported.

All immunogenicity variables have a lower limit of quantification (LLOQ). Results that are <LLOQ will be imputed as the limit of detection (LOD) in calculations of summary statistics in tabular and graphical displays. The CRM197-specific IgG and IgM assays have a 3-fold titration series, so the imputed value will be  $LOD = 1/3 * LLOQ$ . The *C. jejuni* capsule-specific serum IgG and IgM and ALS IgG assays have a 2-fold titration series, so the imputed value will be  $LOD = 1/2 * LLOQ$ . Imputed values will be rounded to the nearest whole number for consistency with conversion of results from  $\log_{10}$  titer to titer. The number of results <LLOQ will be reported in tabular summaries.

Immune Response	LLOQ		
	Log 10 Titer	Titer	Imputed Titer when <LLOQ
C. Jejuni Capsule-specific IgG Serum Antibody	2.30	200	100
C. Jejuni Capsule-specific IgM Serum Antibody	2.30	200	100
CRM 197 -specific IgG Serum Antibody	3.00	1000	333
CRM 197 -specific IgM Serum Antibody	2.00	100	33
C. Jejuni Capsule-specific IgG ALS Antibody	0.70	5	3

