### 9.3. Adverse Events

When calculating the incidence of adverse events (i.e., on a per participant basis), each participant will only be counted once per AE using the event with maximum severity and any repetitions of adverse events within a participant will be ignored; the denominator will be the total number of participants receiving the specified vaccination. All unsolicited adverse events reported will be included in [Listing 11](#).

An overall summary of adverse events will be presented in [Table 30](#). A table of all SAEs and non-serious AEs occurring in at least 5% of participants in any treatment group will be presented by MedDRA SOC and PT and treatment group in [Table 31](#).

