### 9.3.1.     Solicited Events and Symptoms

Temperatures collected on the Vital Signs eCRF within 7 days following vaccination will be considered towards the solicited AE of fever and will be included in all tables, figures, and listings summarizing solicited AEs.

The number and percentage with 95% CI of participants reporting at least one solicited adverse event of at least mild severity within 7 days following vaccination will be summarized for each solicited symptom, any systemic symptom, any local symptom, and any symptom following each vaccination and following any vaccination for Cohort 1 ([Table 32](#)), Cohort 2 ([Table 33](#)), and Cohort 3 ([Table 34](#)). The 95% CI will be calculated using Clopper-Pearson methodology from a binomial distribution (SAS Proc Freq with a binomial option).

For each systemic and local symptom, any systemic symptom, any local symptom, and any solicited symptom, the number and percentage of participants reporting the symptom will be summarized by severity for each day and maximum severity within 7 days after each vaccination for Cohort 1 for vaccination 1 ([Table 35](#)), vaccination 2 ([Table 36](#)), vaccination 3 ([Table 37](#)), and any vaccination ([Table 38](#)). Analogous tables for each vaccination and any vaccination will be presented for Cohort 2 ([Table 39](#), [Table 40](#), [Table 41](#), and [Table 42](#)) and Cohort 3 ([Table 43](#), [Table 44](#), [Table 45](#), and [Table 46](#)). For each event the denominator is the number of participants with non-missing data for the specific event.

The percentage of participants reporting any solicited systemic symptom will be summarized graphically in a bar chart by maximum severity, day post vaccination, and vaccination group for each vaccination ([Figure 32](#), [Figure 33](#), and [Figure 34](#)) and for all vaccinations combined ([Figure 35](#)). Analogous figures will be presented for any solicited local symptom ([Figure 36](#), [Figure 37](#), [Figure 38](#), and [Figure 39](#)).

The percentage of participants experiencing each solicited symptom within 7 days of vaccination will be summarized in a bar chart by maximum severity and treatment group for each vaccination ([Figure 40](#), [Figure 41](#), and [Figure 42](#)) and for all vaccinations combined ([Figure 43](#)).

All solicited adverse events will be presented by participant in [Listing 9](#) for systemic symptoms and [Listing 10](#) for local symptoms.

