	Any Vac	x	x	xx	xx, xx	x	x	xx	xx, xx

Notes: N = Number of participants in the Safety Population who received the specified vaccination.

a Reported from time of vaccination through 7 days post vaccination.

b Exact 95% Clopper-Pearson confidence interval.

c Chills/shivering/sweating.

Tables with similar format:

**Table 33: Number and Percentage of Participants Experiencing Solicited Events with 95% Confidence Intervals by Symptom and Vaccination - Cohort 2**

**Table 34: Number and Percentage of Participants Experiencing Solicited Events with 95% Confidence Intervals by Symptom and Vaccination - Cohort 3**

**Table 35: Number and Percentage of Participants Experiencing Solicited Events by Symptom, Severity, Day Relative to Vaccination, and Treatment Group - Cohort 1, Vaccination 1**

*[Implementation Note: The “Post Vac” time point is the in-clinic assessment 30 minutes after vaccination, and Day 1 is from the memory aid completed by the participant for the day of vaccination. If there are any time points with at least 1 participant with a symptom that was not assessed, remove (N=X) from the header of each treatment group and add a column labelled “N” before the “None” category for each treatment group. Update the “N =” footnote to “N = Number of participants in the Safety Population who received the specified vaccination and were assessed for the given symptom at the given time point.”.]*

Symptom	Day Relative to Vaccination	1 ug CJC2V (N=X)								1 ug CJC2V+ALFQ (N=X)							
		None		Mild		Moderate		Severe		None		Mild		Moderate		Severe	
		n	%	n	%	n	%	n	%	n	%	n	%	n	%	n	%
Any Symptom	Pre-Vac	x	xx	x	xx	x	xx	x	xx	x	xx	x	xx	x	xx	x	xx
	Post Vac	x	xx	x	xx	x	xx	x	xx	x	xx	x	xx	x	xx	x	xx
	Day 1	x	xx	x	xx	x	xx	x	xx	x	xx	x	xx	x	xx	x	xx
	Day 2	x	xx	x	xx	x	xx	x	xx	x	xx	x	xx	x	xx	x	xx
	Day 3	x	xx	x	xx	x	xx	x	xx	x	xx	x	xx	x	xx	x	xx
	Day 4	x	xx	x	xx	x	xx	x	xx	x	xx	x	xx	x	xx	x	xx
	Day 5	x	xx	x	xx	x	xx	x	xx	x	xx	x	xx	x	xx	x	xx
	Day 6	x	xx	x	xx	x	xx	x	xx	x	xx	x	xx	x	xx	x	xx
	Day 7	x	xx	x	xx	x	xx	x	xx	x	xx	x	xx	x	xx	x	xx
	Day 8	x	xx	x	xx	x	xx	x	xx	x	xx	x	xx	x	xx	x	xx
Systemic Symptoms	Maximum	x	xx	x	xx	x	xx	x	xx	x	xx	x	xx	x	xx	x	xx
	Pre-Vac	x	xx	x	xx	x	xx	x	xx	x	xx	x	xx	x	xx	x	xx
	Post Vac	x	xx	x	xx	x	xx	x	xx	x	xx	x	xx	x	xx	x	xx
	Day 1	x	xx	x	xx	x	xx	x	xx	x	xx	x	xx	x	xx	x	xx
	Day 2	x	xx	x	xx	x	xx	x	xx	x	xx	x	xx	x	xx	x	xx

Symptom	Day Relative to Vaccination	1 ug CJC2V (N=X)								1 ug CJC2V+ALFQ (N=X)							

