### 14.3.1.1      **Solicited Adverse Events**

**Figure 32:      Maximum Severity of Any Solicited Systemic Symptom per Participant by Treatment Group and Day Relative to Vaccination, Vaccination 1**

*[Implementation note: The figure below is an example only. N is the number of participants in the Safety Population receiving specified vaccination. Post Vac is the in-clinic assessment 30 minutes after vaccination, and Day 1 is from the memory aid completed by the participant for the day of vaccination. Update footnotes with applicable vaccination number. If the figure is difficult to read, each figure in this section may be split into 3 separate figures by cohort.]*

Notes: N = Number of participants in the Safety Population receiving Vaccination 1.

Post Vac is the in-clinic assessment 30 minutes after vaccination; Day 1 is from the memory aid completed by the participant for the day of vaccination.

Figures with similar format:

**Figure 33:** Maximum Severity of Any Solicited Systemic Symptom per Participant by Treatment Group and Day Relative to Vaccination, Vaccination 2

**Figure 34:** Maximum Severity of Any Solicited Systemic Symptom per Participant by Treatment Group and Day Relative to Vaccination, Vaccination 3

**Figure 35:** Maximum Severity of Any Solicited Systemic Symptom per Participant by Treatment Group and Day Relative to Vaccination, Any Vaccination

**Figure 36:** Maximum Severity of Any Solicited Local Symptom per Participant by Treatment Group and Day Relative to Vaccination, Vaccination 1

[figure not shown]
**Figure 37:** Maximum Severity of Any Solicited Local Symptom per Participant by Treatment Group and Day Relative to Vaccination, Vaccination 2

**Figure 38:** Maximum Severity of Any Solicited Local Symptom per Participant by Treatment Group and Day Relative to Vaccination, Vaccination 3

**Figure 39:** Maximum Severity of Any Solicited Local Symptom per Participant by Treatment Group and Day Relative to Vaccination, Any Vaccination

**Figure 40: Maximum Severity of Solicited Symptoms within 7 Days of Vaccination by Treatment Group and Symptom, Vaccination 1**

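### Solicited-event percentages have two conflicting denominators; if post-clinic data are missing, the tables carrying the primary-endpoint confidence intervals count that person as event-free

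*SAP*

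**What the plan says.** Solicited local and systemic events through 7 days after each vaccination are the first primary endpoint (SAP 3.2). The SAP states the divisor for their percentages in several places.

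**All vaccinated**
- SAP 9.3, on adverse-event incidence generally: "the denominator will be the total number of participants receiving the specified vaccination".
- Table 32 footnote (Tables 33 and 34 share the format): "N = Number of participants in the Safety Population who received the specified vaccination". There is no alternative for missing data.
- Figure 32 note: "N is the number of participants in the Safety Population receiving specified vaccination". The Figure 40 note is equivalent.

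**Non-missing or assessed**
- SAP 6.1: "percentages (%; based on the non-missing sample size) of observed levels will be reported for all categorical measures".
- SAP 9.3.1, closing the paragraph on Tables 35–46: "For each event the denominator is the number of participants with non-missing data for the specific event".
- Table 35 note: N is all vaccinated by default. If any symptom went unassessed, N becomes those "who received the specified vaccination and were assessed for the given symptom at the given time point".

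SAP 9.3.2 separately specifies all vaccinated for unsolicited events. SAP 6.5 expects little missing data and says "no imputation will be performed for missing values". No section defines what counts as non-missing when a 7-day window is only partly recorded.

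**The concern.** Tables 32–34 are the only solicited tables with confidence intervals. The primary outcome is descriptive (SAP 6.8), so those percentages and intervals are the result. Under an all-vaccinated divisor, a participant with no usable data stays in N but cannot enter n. For reactogenicity that is the unsafe direction, and each person is 10% of a planned arm.

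There is also a reproducibility problem. The mild, moderate and severe counts in a 'Maximum' row of Tables 35–46 add up to the any-event count in the matching row of Tables 32–34. If the two table sets use different divisors, one study report can show two percentages for the same quantity, with no rule for which to cite.

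**Working it through.** **Inputs.** Ten participants per arm and exact two-sided 95% Clopper-Pearson limits (SAP 5, 6.1, 9.3.1). The number with no usable data, m, is an assumption, since the documents give none; m = 0 to 3 is shown.

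**The plan's own figure.** For zero events the upper limit is 1 − 0.025^(1/n). With n = 10 this is 1 − 0.025^(0.1) = 30.8%, which reproduces the stated 0–31%.

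**Effect of the divisor.** For x events the two versions are x/10 and x/(10 − m). For 0 < x < n, the limits are the 2.5% quantile of Beta(x, n − x + 1) and the 97.5% quantile of Beta(x + 1, n − x).

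| m | 0 events | 3 events | 5 events |
|---|---|---|---|
| 0 (all vaccinated, or complete data) | 0% (0–30.8) | 30.0% (6.7–65.2) | 50.0% (18.7–81.3) |
| 1 | 0% (0–33.6) | 33.3% (7.5–70.1) | 55.6% (21.2–86.3) |
| 2 | 0% (0–36.9) | 37.5% (8.5–75.5) | 62.5% (24.5–91.5) |
| 3 | 0% (0–41.0) | 42.9% (9.9–81.6) | 71.4% (29.0–96.3) |

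With m = 1 and five events, the all-vaccinated divisor gives 5/10 = 50% and the assessed divisor gives 5/9 = 56%. The difference of 5.6 points sits inside an interval 81.3 − 18.7 = 62.6 points wide.

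**Expected bias.** Suppose the true rate is p and a fraction q has no usable data for reasons unrelated to the event. The all-vaccinated estimate then has mean p(1 − q), a bias of −pq. At p = 50% this is −2.5, −5 and −10 points for q = 5%, 10% and 20%. At p = 30% it is −1.5, −3 and −6 points. At q = 0 it is zero.

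**Without that assumption.** With five events observed and one of 10 missing, the complete-data rate would be 5/10 or 6/10, that is, 50% or 60%. The all-vaccinated figure is the lower bound.

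**Who could be missing.** Table 32 counts any symptom from vaccination onward, including the clinic check at 30 minutes. Every listed symptom except fever has that row in Table 35. For fever, temperatures on the vital-signs form within 7 days also count (SAP 9.3.1). In Cohorts 2 and 3, however, Day 3 vital signs were taken only if indicated (SAP 9.7). Someone without a diary may therefore have only the Day 8 clinic temperature.

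**The case against.** The strongest reply is that this is two rules for two kinds of table. By-day rows need time-point denominators, while any-event incidence per vaccination can reasonably use the Safety Population. The 9.3.1 sentence closes the paragraph on the by-day tables, and the Table 32 footnote follows 9.3. That reading is fair, but it does not reconcile Section 6.1, and the 'Maximum' rows still repeat the quantity in Tables 32–34.

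A second reply is that a missing diary is not a missing participant. Solicited symptoms are checked in clinic about 30 minutes after each vaccination. Staff must review the diary and interview the participant at the next visit, a paper aid is the back-up, and the reviewed eCRF data, not the diary, are the source (Protocol 10). This stands, and it limits the size of the problem. It also means that, if the 30-minute check alone counts as non-missing, the two table sets would usually agree for symptoms other than fever. But someone seen only at 30 minutes would then be event-free in both.

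A reader might infer that the SAP scores a missing diary as no event, contrary to Section 6.5. It does not say so. Section 6.5 concerns filling in values, and a Safety Population denominator fills in none; the resemblance is in effect only.

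The halting rules count subjects rather than percentages (Protocol 7.6), and Listings 9 and 10 show every solicited event by participant, so neither is affected.

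**Conclusion.** The denominator conflict is real and falls on the main table for a primary safety endpoint. If post-clinic data are missing, Tables 32–34 can only understate the rate and its upper limit relative to participants who were assessed. Assuming one of 10 is missing, five events read 50% instead of 56%, and the zero-event upper limit reads 30.8% instead of 33.6%. The missing count is assumed; with complete data the denominators coincide.

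A reader might go further and infer that this trial's reactogenicity rates will be biased down. The documents do not support that: they expect minimal missing data, report no missing-diary count and provide several routes to recover symptoms. The effect is likely small, with fever most exposed. This is a low-priority but worthwhile correction. Making it before unblinding avoids a later choice between two percentages.

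**What to change.** 1. Use one N for the rows of Tables 32–34, the 'Maximum' rows of Tables 35–46 and Figures 40–43: participants who received the vaccination and have at least one assessment of that symptom after leaving the clinic (a diary day or staff-confirmed information) within the 7-day window. Anyone reporting an event is always included. For fever, state whether a single Day 8 clinic temperature is enough.
2. Show the assessed n beside the vaccinated N.
3. Keep the time-point-specific assessed denominator for the by-day rows of Tables 35–46, and match Figures 32–39 to it. A window-level N there would keep someone who missed one day in that day's divisor.
4. Keep all vaccinated for unsolicited events.
5. Align SAP 9.3, 9.3.1 and the footnotes with these rules.

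Requiring an assessment after the clinic matters: a rule of assessed at least once would be met by the 30-minute check for every symptom except fever and would change almost nothing.

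The cost is SAP wording and shell footnotes, with slightly wider intervals when diaries are missing. Two limits remain. One diary day is still a thin basis for calling someone event-free. Always including reported events leans slightly upward when a person has only clinic data. Printing both N and n lets the reader see the extent of each.

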### 9.3.2.     Unsolicited Adverse Events

The number and percentage with 95% CI of participants reporting at least one unsolicited adverse event along with the total frequency of unsolicited adverse events will be summarized by MedDRA SOC and PT, vaccination, and treatment group for each cohort ([Table 47](#) for Cohort 1, [Table 48](#) for Cohort 2, and [Table 49](#) for Cohort 3). Denominators for percentages are the number of participants who received the vaccination being summarized.

The number and percentage of participants experiencing unsolicited adverse events along with the frequency of events will be reported by MedDRA SOC and PT, relationship, severity, and treatment group for Cohort 1 for each vaccination ([Table 50](#), [Table 51](#), and [Table 52](#)) and any vaccination ([Table 53](#)). Analogous tables will be presented for Cohort 2 ([Table 54](#), [Table 55](#), [Table 56](#), and [Table 57](#)) and Cohort 3 ([Table 58](#), [Table 59](#), [Table 60](#), and [Table 61](#)).

Bar charts will graphically display the frequency of related unsolicited adverse events by MedDRA SOC, severity, and treatment group for each vaccination ([Figure 44](#), [Figure 45](#), and [Figure 46](#)) and any vaccination ([Figure 47](#)). Analogous bar charts will display the incidence of related unsolicited adverse events ([Figure 48](#), [Figure 49](#), [Figure 50](#), and [Figure 51](#)).

Listings of individual events including participant ID, AE description, associated vaccination, onset and duration of AE, severity, relationship (and alternate etiology if Not Related), action taken with study vaccinations, outcome, and MedDRA SOC and PT will be provided for non-serious unsolicited AEs of moderate or greater severity ([Table 63](#)).

All reported unsolicited adverse events will be presented in [Listing 11](#).

## 9.4. Deaths, Serious Adverse Events and other Significant Adverse Events

The following listings will be presented including participant ID, AE description, associated vaccination, AE onset and duration, reason reported as an SAE (for SAEs only), severity, relationship to study vaccine (and alternative etiology if Not Related), action taken with study vaccinations, outcome, and MedDRA SOC and PT:

- Deaths and other Serious Adverse Events ([Table 62](#)).
- Medically Attended Adverse Events (MAAEs), New Onset Chronic Medical Conditions (NOCMCs), and Potentially Immune-Mediated Medical Conditions (PIMMCs) ([Table 64](#)).

## 9.5. Pregnancies

For any participants in the Safety population who become pregnant during the study, every attempt will be made to follow these participants to completion of pregnancy to document the outcome, including information regarding any complications with pregnancy and/or delivery. Listings of all pregnancies and outcomes will be presented ([Listing 17](#), [Listing 18](#), [Listing 19](#), [Listing 20](#), and [Listing 21](#)).

## 9.6. Clinical Laboratory Evaluations

Laboratory AEs will be graded according to the scale presented in [Table 7](#). Chemistry parameters will include creatinine, ALT, total bilirubin, sodium, and potassium. Hematology parameters will include Hgb, WBC, ANC, and platelets.

All chemistry results for participants with at least one abnormal chemistry result will be listed in [Table 65](#). An analogous table for participants with at least one abnormal hematology result will be listed in [Table 66](#).

The distribution of laboratory results by time point, treatment group, relationship (Total and Related), and severity will be presented for any chemistry parameter ([Table 67](#)) and for each parameter ([Table 68](#), [Table 69](#), [Table 70](#), [Table 71](#), and [Table 72](#)). Analogous results will be presented for any hematology parameter ([Table 79](#)) and for each hematology parameter ([Table 80](#), [Table 81](#), [Table 82](#), and [Table 83](#)).

Descriptive statistics including mean, standard deviation, median, minimum, and maximum will be summarized by time point and treatment group for each chemistry parameter ([Table 73](#), [Table 74](#), [Table 75](#), [Table 76](#), [Table 77](#), and [Table 78](#)) and each hematology parameter ([Table 84](#), [Table 85](#), [Table 86](#), [Table 87](#), and [Table 88](#)); the change from baseline values will also be summarized for post-baseline time points.

[Listing 12](#) and [Listing 13](#) will provide a complete listing of individual clinical laboratory results with applicable reference ranges for chemistry and hematology results respectively.

## 9.7. Vital Signs and Physical Evaluations

Vital sign measurements will include systolic blood pressure, diastolic blood pressure, pulse, and oral temperature. Vital signs will be assessed at screening (Day -30 to -2), Day 1, Day 8, Day 29, Day 36, Day 57,

Day 64, Day 85, and Day 113 for all Cohorts. Cohort 1 was enrolled and completed follow-up under protocol v4.0 (25MAY2022) which also required collection of vital signs at Day 3, Day 15, Day 31, Day 43, Day 59, and Day 71; in the later versions of the protocol followed by Cohorts 2 and 3, vital signs were only collected on these days if indicated. The tables and listing described in this section will only include vital signs collected in clinic on the Vital Signs eCRF. Vital Signs will be graded according to the scale in [Table 6](#).

Vital signs will be tabulated by severity, time point, and treatment group for any assessment ([Table 89](#)) and for each assessment ([Table 90](#), [Table 91](#), [Table 92](#), and [Table 93](#)). Summary statistics of vital signs will be presented for each assessment by time point and treatment group ([Table 94](#), [Table 95](#), [Table 96](#), and [Table 97](#)). All vital signs will be listed by participant and time point ([Listing 14](#)).

An abbreviated physical examination will be performed at screening (Day -30 to -2), and targeted physical exams will be performed as indicated at subsequent visits. The following body systems will be assessed in the abbreviated physical exam: general appearance, skin, head and neck, lungs, heart, liver, spleen, extremities, musculoskeletal and lymph nodes; the targeted physical exam will only include the relevant body systems. All abnormal findings will be listed by participant and time point ([Listing 15](#)).

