## 4.3. Selection of Study Population

Cohort 1 was enrolled under protocol v4.0 (25MAY2022), and Cohorts 2 and 3 were enrolled under protocol v6.0 (08MAY2023); the full list of inclusion and exclusion criteria can be found in the specified versions of the protocol. The inclusion and exclusion criteria were updated between the enrollment of Cohort 1 and Cohort 2 to be less restrictive. The major differences are listed below:

- The inclusion criteria in v4.0 required a Body Mass Index (BMI) < 36; this was changed to BMI < 40 in v6.0.
- The exclusion criteria in v4.0 excluded participants with “documented family history of auto-immune conditions”; this was changed to “documented history of auto-immune conditions in a first-degree relative” in v6.0.
- The exclusion criteria in v4.0 excluded participants with “travel to countries with high *Campylobacter* rates (to include Asia, Africa, and Central and South America) within two years prior to dosing.” This exclusion criterion was removed in v6.0.

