## 5. SAMPLE SIZE CONSIDERATIONS

Sixty (60) participants will be enrolled (20 per cohort). The sample size for each cohort was chosen based on the number of participants deemed appropriate for a first-in-human Phase 1 study. Given the small number of participants per group, the precision of our estimate for adverse events is limited. For example, using an exact binomial interval for no observed adverse events within the 10 participants per group yields a 95% confidence interval (CI) of 0-31% (Clopper-Pearson) ([Table 3](#)). Follow-on studies evaluating seemingly safe and immunogenic doses will be required with larger numbers of volunteers in order to better define the safety profile.

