## **6.8. Multiple Comparisons/Multiplicity**

The primary outcome is descriptive. No testing or adjustments for multiple testing are planned.

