### 14.3.6 Displays of Vital Signs

**Table 89: Vital Signs by Time Point, Treatment Group, and Severity – Any Assessment**

*[Implementation Note: Participants will be counted as “Missing” if they are still under follow-up and do not have a result reported; if the “Missing” column only contains 0 values, it may be removed from the table. If all vital signs are “None” at the Pre-Vaccination 1 (Study Day 1) time point, that time point may be removed from the table. Unscheduled visits will only be considered in the “Max Severity Post Baseline” time point. For Temperature, only include the temperature measurements taken in-clinic and entered on the Vital Signs eCRF in this table (i.e., do not consider events from the participant’s eMemory Aid).]*

Time Point	Treatment Group	N	None n (%)	Mild n (%)	Moderate n (%)	Severe n (%)	Missing n
Pre-Vaccination 1 (Study Day 1)	1 µg CJC2	x	x (xx)	x (xx)	x (xx)	x (xx)	x
	1 µg CJC2+ALFQ	x	x (xx)	x (xx)	x (xx)	x (xx)	x
	3 µg CJC2	x	x (xx)	x (xx)	x (xx)	x (xx)	x
	3 µg CJC2+ALFQ	x	x (xx)	x (xx)	x (xx)	x (xx)	x
	10 µg CJC2	x	x (xx)	x (xx)	x (xx)	x (xx)	x
	10 µg CJC2+ALFQ	x	x (xx)	x (xx)	x (xx)	x (xx)	x
2 Days Post Vaccination 1 (Study Day 3) a	1 µg CJC2	x	x (xx)	x (xx)	x (xx)	x (xx)	x
	1 µg CJC2+ALFQ	x	x (xx)	x (xx)	x (xx)	x (xx)	x
7 Days Post Vaccination 1 (Study Day 8)	1 µg CJC2	x	x (xx)	x (xx)	x (xx)	x (xx)	x
	1 µg CJC2+ALFQ	x	x (xx)	x (xx)	x (xx)	x (xx)	x
	3 µg CJC2	x	x (xx)	x (xx)	x (xx)	x (xx)	x
	3 µg CJC2+ALFQ	x	x (xx)	x (xx)	x (xx)	x (xx)	x
	10 µg CJC2	x	x (xx)	x (xx)	x (xx)	x (xx)	x
	10 µg CJC2+ALFQ	x	x (xx)	x (xx)	x (xx)	x (xx)	x
14 Days Post Vaccination 1 (Study Day 15) a	1 µg CJC2	x	x (xx)	x (xx)	x (xx)	x (xx)	x
	1 µg CJC2+ALFQ	x	x (xx)	x (xx)	x (xx)	x (xx)	x
Pre-Vaccination 2 (Study Day 29)	1 µg CJC2	x	x (xx)	x (xx)	x (xx)	x (xx)	x
	1 µg CJC2+ALFQ	x	x (xx)	x (xx)	x (xx)	x (xx)	x

Time Point	Treatment Group	N	None n (%)	Mild n (%)	Moderate n (%)	Severe n (%)	Missing n
	3 µg CJC2	x	x (xx)	x (xx)	x (xx)	x (xx)	x
	3 µg CJC2+ALFQ	x	x (xx)	x (xx)	x (xx)	x (xx)	x
	10 µg CJC2	x	x (xx)	x (xx)	x (xx)	x (xx)	x
	10 µg CJC2+ALFQ	x	x (xx)	x (xx)	x (xx)	x (xx)	x
2 Days Post Vaccination 2 (Study Day 31) a	1 µg CJC2	x	x (xx)	x (xx)	x (xx)	x (xx)	x
	1 µg CJC2+ALFQ	x	x (xx)	x (xx)	x (xx)	x (xx)	x
7 Days Post Vaccination 2 (Study Day 36)	1 µg CJC2	x	x (xx)	x (xx)	x (xx)	x (xx)	x
	1 µg CJC2+ALFQ	x	x (xx)	x (xx)	x (xx)	x (xx)	x
	3 µg CJC2	x	x (xx)	x (xx)	x (xx)	x (xx)	x

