Participants are counted once per time point.							
a Cohort 1 was enrolled and completed follow-up under v4.0 of the protocol which required collection of vital signs at this time point which was not required beginning in v5.0 of the protocol.							
b Indicates the maximum severity experienced by each participant at any time point post first vaccination, including unscheduled assessments.							

Table with similar format:

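### SAP Tables 89–93: the maximum-severity row sets doses side by side over up to 13 scheduled vital-sign days at 1 µg but 7 at 3 and 10 µg, with no note on that row and no maximum over the common days

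*SAP*

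**What the plan says.** SAP 9.7 lists Days 8, 29, 36, 57, 64, 85 and 113 as post-baseline vital-sign days for all cohorts. It adds that Cohort 1 followed protocol v4.0, "which also required collection of vital signs at Day 3, Day 15, Day 31, Day 43, Day 59, and Day 71". Under the later versions followed by Cohorts 2 and 3, "vital signs were only collected on these days if indicated". The section also limits these tables to in-clinic readings on the Vital Signs eCRF.

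The shells for Tables 89 and 91 (Tables 90, 92 and 93 share their formats) handle the difference row by row. The six extra days appear for the 1 µg groups only and carry footnote a: "Cohort 1 was enrolled and completed follow-up under v4.0 of the protocol which required collection of vital signs at this time point".

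The last row, *Max Severity Post Baseline*, lists all six groups and carries footnote b: "Indicates the maximum severity experienced by each participant at any time point post first vaccination, including unscheduled assessments". The implementation note adds a further source that feeds this row and no other: "Unscheduled visits will only be considered in the" maximum row.

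Neither SAP 9.7, the shells nor SAP section 15 plans a maximum restricted to the days that all cohorts share.

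**The concern.** A maximum cannot fall, and usually rises, as readings are added. Each cohort is a single dose level, so the schedule change is completely confounded with dose. This is the one row in these tables that sums up each group over the whole study, and in it the lowest dose had the most scheduled chances to show a graded value.

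If true risk were the same at every dose, the 1 µg groups would tend to show more graded maxima than the 3 and 10 µg groups. Someone reading the row across doses in the study report could then miss or underrate a dose trend. The plan recognises the imbalance on the day rows and then combines the same readings, unflagged, in the summary row.

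**Working it through.** **The plan's own precision figure.** SAP section 5 gives a 95% interval of 0–31%, "using an exact binomial interval for no observed adverse events within the 10 participants per group". Check: 1 − 0.025^(1/10) = 0.308. It reproduces, and it confirms the displayed group size of 10 (3 sentinels + 7, SAP Table 1).

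**Scheduled days, counted from SAP 9.7.**
- Common to all cohorts: 8, 29, 36, 57, 64, 85, 113 = 7.
- Cohort 1 only: 3, 15, 31, 43, 59, 71 = 6.
- Cohort 1 total: 7 + 6 = 13. Cohorts 2 and 3: 7.

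Day 1 is the pre-vaccination baseline and is not counted.

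**Illustration of size.** The documents give no chance q that a single reading is graded and no within-person correlation ρ, so both are assumed, with true risk equal at every dose.
- Independent readings (ρ = 0): P(any graded) = 1 − (1 − q)^n.
- Correlated readings: beta-binomial with a + b = (1 − ρ)/ρ and a = q(a + b), so P(none in n) = ∏ (b + i)/(a + b + i) for i = 0 to n − 1.

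Example at q = 2%, ρ = 0: 1 − 0.98^13 = 0.231 and 1 − 0.98^7 = 0.132. In a group of 10 the difference is 10 × (0.231 − 0.132) = 0.99.

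| q | ρ | P, 13 days | P, 7 days | Excess per 10 |
|---|---|---|---|---|
| 2% | 0 | 0.231 | 0.132 | 0.99 |
| 2% | 0.1 | 0.155 | 0.103 | 0.52 |
| 2% | 0.5 | 0.062 | 0.051 | 0.11 |
| 5% | 0 | 0.487 | 0.302 | 1.85 |
| 5% | 0.1 | 0.346 | 0.241 | 1.05 |
| 5% | 0.5 | 0.149 | 0.123 | 0.25 |

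Independence is the upper case, because repeated readings on one person are normally correlated.

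**Effect of if-indicated readings.** Suppose 2 of the 6 extra days were read for everyone in Cohorts 2 and 3 (n = 13 against 9). The excess at q = 2% falls to 0.65, 0.32 and 0.07 for ρ = 0, 0.1 and 0.5.

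**After restriction to the seven common days.** Every group has n = 7, so at equal risk the expected share is the same at every dose (0.132 at q = 2%, ρ = 0).

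**Vital-sign adverse events through Day 85 (28 days after the last dose).** SAP 4.5.1 makes a graded worsening from baseline an unsolicited event, except for temperatures from vaccination through 7 days afterwards, which are solicited. At nominal visit days:
- Pulse and blood pressure: 13 − 1 = 12 scheduled checks in Cohort 1 against 7 − 1 = 6 in Cohorts 2 and 3 (Day 113 drops out).
- Temperature: Days 3, 8, 31, 36, 59 and 64 fall in the solicited window. That leaves 6 (Days 15, 29, 43, 57, 71, 85) against 3 (Days 29, 57, 85).

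No effect on event counts is computed, since such an event must also be worse than baseline.

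**The case against.** The strongest reply is that the schedule change is already disclosed. SAP 9.7 states it in the text, footnote a sits directly above footnote b, the extra-day rows visibly contain only the 1 µg groups, and Listing 14 gives every reading. This stands in part, and a reader should not infer that the difference is concealed. But the maximum row points only to footnote b, and the by-visit counts cannot be combined into a per-participant maximum without going back to the listing.

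Second, scheduled days are not realised readings. Only in-clinic readings enter these tables. The current protocol allows the 3- and 15-day visits to be virtual and the v4.0 text is not available, so Cohort 1 may have fewer than 13. If-indicated and unscheduled readings in Cohorts 2 and 3 can add to 7. This stands: the true gap is unknown. Readings taken for cause do not, however, restore equal detection.

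Third, little depends on the row. SAP 6.8 says "No testing or adjustments for multiple testing are planned", vital-sign maxima are not an endpoint, and the doses were not randomised against each other. SAP 4.3 also notes that "The inclusion and exclusion criteria were updated between the enrollment of Cohort 1 and Cohort 2 to be less restrictive". All of this stands, so equalising the days would not by itself make the cohorts comparable.

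A reader might also extend the point to Tables 30 and 31 and say that all vital-sign adverse events were detected under 12 against 6 scheduled checks. The documents do not support that. Temperatures in the 7 days after each vaccination are solicited events and are also recorded daily on the memory aid, so 12 against 6 holds only for pulse and blood pressure.

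**Conclusion.** The point holds as a limited reporting weakness. The maximum row of Tables 89–93 compares doses under unequal scheduled detection, up to 13 days against 7. The footnote on that row is silent about it, and no like-for-like maximum is planned. The expected direction, at equal true risk, is to make 1 µg look worse relative to 3 and 10 µg.

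The size is not known. On assumed rates of 2% and 5% per reading, with correlation from 0.5 down to 0, the excess is about 0.1 to 1.0 and 0.3 to 1.9 participants per group of 10. These figures assume that the realised readings equal the scheduled days. For scale, zero events in 10 already leaves an upper limit of 31%.

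It would be tempting to conclude that the trial's safety findings across doses are biased by a known amount. The documents do not support this: no rate is given, the display is descriptive, and other differences between cohorts remain. The by-visit rows for the common days, Listing 14 and the comparison with and without ALFQ within each cohort are unaffected. This is a cheap improvement and no threat to the trial's conclusions.

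**What to change.** In Tables 89–93:
- Add a row *Max Severity, common scheduled days*, limited to Days 8, 29, 36, 57, 64, 85 and 113 in every cohort, and use it for reading across doses.
- Keep the all-readings maximum, so that no severe value is lost.
- Extend footnote b to state 13 scheduled post-baseline days in Cohort 1 and 7 in Cohorts 2 and 3, plus unscheduled or if-indicated in-clinic readings.

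Tables 30 and 31 need no blanket note. If one is added, it should give 12 against 6 scheduled checks through Day 85 for pulse and blood pressure only, and 6 against 3 for unsolicited temperature events. No adverse event should be removed.

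The vital-sign wording for the 3- and 15-day visits should also be reconciled. Protocol 5.3.1 lists vital signs among procedures to be done as applicable, Appendix A has no mark at those visits, and SAP 9.7 makes them conditional on indication.

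The cost is one extra row in each of five tables and a longer footnote, from readings already on the Vital Signs eCRF. No new data are needed; the only downside is slightly longer tables.
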